2. STUDY OBJECTIVES

2.1. Primary Objective

The primary objectives of this study are to assess:

- The long-term safety of CCH in the treatment of EFP commonly known as cellulite in adult women
- The safety of CCH when used for retreatment in the treatment of EFP commonly known as cellulite in adult women
- The long-term immunogenicity profile of CCH following treatment of EFP commonly known as cellulite in adult women

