3.11. Safety Assessments

3.11.1. Adverse Events (AE)

All Adverse Events (AE) occurring after signing the informed consent are to be recorded on the AE pages of the case report form (CRF). This includes any new signs, symptoms, injury or illness, including increased severity of previous existing signs, symptoms, injury, or illness. Any medical conditions occurring between completion of the double-blind studies and the screening visit of this study will be considered AE and will be recorded and evaluated for seriousness. The ongoing AE's from EN3835 302/303 studies at the time screening of this study will also be imported.

Adverse Events (AE)

An AE is any unfavorable or unintended change in body structure (signs), body function (symptoms), laboratory result (eg, chemistry, ECG, X-ray, etc.), or worsening of a pre-existing condition associated temporally with the use of the study medication whether or not considered related to the study medication. This would include AEs resulting from concurrent illness, reactions to concurrent medication use, or progression of disease states (excluding the disease under study). A condition present at baseline that worsens after initiation of study treatment will be captured as an AE; the onset date will be the date the event worsened.

Serious Adverse Events (SAEs)

Serious adverse event are those AEs that meets any of the following criteria:

- Results in death

- Life-threatening event
- Results in or prolongs an inpatient hospitalization
- Results in permanent or substantial disability
- Is a congenital anomaly or birth defect
- Any important medical event that may jeopardize the patient or may require medical intervention to prevent one of the outcomes listed above

Adverse Events of Special Interest

AEs such as bruising, ecchymosis, hematomas, and contusions that occur remote to the site of drug administration, or any hypersensitivity reactions, including anaphylaxis, will be recorded as an AE of special interest and reported as an AE or SAE as appropriate.

In addition, local AEs associated with the injection site (whether the site was injected in the double-blind study (EN3835-302/303) or in this open-label study (EN3835-304)), including acute (eg, erythema, bruising, pain, nodules/mass, ulceration, erythema, pruritus, swelling, and/or induration) and/or chronic (eg, skin thickening, fibrosclerosis, peau d’orange changes), cutaneous adverse events, will be recorded.

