4.5.1.2. Adverse Events during Open-label Period

Adverse Event Categorization Before Retreatment

The AEs will be associated with time periods in the open label study period based on the start date of the AE compared to time period start date, as below:

- Start of Open-label Period – <Day 360 (M12)
- ≥Day 360 (M12) – <Day 540 (M18)
- ≥Day 540 (M18) – <Day 720 (M24)
- ≥Day 720 (M24) – <Day 1080 (M36)

Adverse Event Categorization after Retreatment

An AE will be associated with a treatment session during the retreatment session based on the start date of the AE compared to the date of the injections.

- AEs (which occur or worsen) with a start date between the Day 1 visit date and the day prior to the next dose or, if no further dose, the Day 71 visit date, will be associated with Treatment Session 1.
- If study drug is administered at the Day 22 visit, AEs (which occur or worsen) with a start date between the Day 22 visit date and the day prior to the next dose or, if no further dose, the Day 71 visit date, will be associated with Treatment Session 2.
- If study drug is administered at the Day 43 visit, AEs (which occur or worsen) with a start date between the Day 43 visit date and the Day 71 visit date will be associated with Treatment Session 3.
- AEs with a start date on or after Day 71 of retreatment will be aligned with observational assessment visits as, AE occurring in time period:
 - ≥Day 71 of retreatment – <Day 360 (M12)
 - ≥Day 360 (M12) – <Day 540 (M18)
 - ≥Day 540 (M18) – <Day 720 (M24)
 - ≥Day 720 (M24) – <Day 1080 (M36)

Refer to section [6.3.1.1](#) to identify AE time period status when the start date of an AE is unknown.

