7.7.2. Adverse Events

AE will be summarized by SOC and PT. A subject will only be counted once per SOC and PT.

For AEs by severity grade (mild, moderate, severe), if a subject has multiple events occurring in the same SOC or same PT, then the event with the maximum intensity (ie, severe) will be counted.

For AEs by relationship to study drug, if a subject has multiple events occurring in the same SOC or same PT, the event with the highest association (ie, related) to study drug will be summarized.

AE will be presented in decreasing order of the incidences at SOC level and within each SOC, in decreasing order of the incidences at the PT level.

All AE summary tables will include number of occurrences of the adverse events and the count of subjects experienced the AEs.

AEs during 180-Day Observation Session: The AEs recorded from day of screening (within 14 days after or on Day 71/EOS of double-blind study) until start of Open-label Period and any

ongoing AEs from EN3835-302/303 studies at the time of screening of this study will be summarized by treatment arm (ie, CCH 1.68 mg, Placebo, and Overall) from double-blind studies (EN3835-302/303) using the Day-180 Observational Population and Prior to Day 180 Population.

An overall summary of AE will be presented and will include:

- Any AE
- Any ongoing AEs from EN3835 302/303
- Any AE of special interest
- Any serious AE
- Any mild, moderate and severe AE
- Any EN3835 302/303 study drug related AE
- Any AEs leading to study discontinuation
- Any AEs resulting in death

The following summary tables will be presented by SOC and PT:

- All AEs
- Ongoing AEs from EN3835 302/303
- All 302/303 study drug related AEs
- AEs by Severity
- Serious AEs
- AEs leading to study discontinuation
- AEs resulting in death
- AEs of Special Interest

Serious and most common non-serious AE by order of frequency (Most frequent, 2nd most frequent and 3rd most frequent) will be summarized by PT. Most common non-serious AEs are any preferred term that at least 5% of the subjects reported at least once.

Subject listings of all AEs, serious AEs, AEs leading to study discontinuation, AEs resulting in death and AEs of Special Interest will be provided for subjects in 180 Day Observational Population.

Subject listings of all AEs in 180 Day Observational Period for all screen failure subjects and Prior to Day 180 Population will also be provided.

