AEs Before Retreatment: The new AEs recorded on or after Open-label Period starts but before retreatment in the open-label study will be summarized for subjects in Open-label Observation Population. This will include AEs of all Category I and II subjects recorded before retreatment and AEs of all Category III subjects.

An overall summary of new AE will be presented by subject category (ie, Category I, II, III, and Overall) and by time period as described in section 4.5.1.2, and will include:

- Any new AE
- Any new AE of special interest
- Any new serious AE

- Any new mild, moderate, and severe AE
- Any new AEs leading to study discontinuation
- Any new AEs resulting in death

The following summary tables will be presented by SOC and PT by subject category (ie, Category I, II, III, and Overall):

- All AEs
- AEs by Severity
- Serious AEs
- AEs leading to study discontinuation
- AEs resulting in death
- AEs of Special Interest

Serious and most common non-serious AE by order of frequency (Most frequent, 2nd most frequent and 3rd most frequent) will be summarized by PT. Most common non-serious AEs are any preferred term that at least 5% of the subjects reported at least once.

Subject listings of all AEs, serious AEs, AEs leading to study discontinuation, AEs resulting in death and AEs of Special Interest will be provided.

AEs During and after Retreatment: The new AEs recorded on or after retreatment in the open label study will be summarized for subjects in OLR Population. This will include AEs of all Category I and II subjects recorded after retreatment.

An overall summary of new AE and new AE related to study drug recorded after retreatment will be presented for each subject category (ie, Category I, II and Overall) by treatment sessions and time period (ie, all study periods and each study period as described in section 4.5.1.2), and will include:

- Any new AE
- Any new AE of special interest
- Any new serious AE
- Any new mild, moderate, and severe AE
- Any new AEs leading to study drug withdrawn/interruption
- Any new AEs leading to study discontinuation
- Any new AEs resulting in death

The following summary tables will be presented by SOC and PT by subject category (ie, Category I, II, and overall) and each treatment sessions [TX1, TX2, TX3, and Total ('Total' includes AEs reported during Treatment Session 1, 2, and 3, and Observation Period post Day 71 of retreatment)]:

- All AEs
- AEs by causal relationship to study drug
- AEs by Severity

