- Study drug related AEs by severity
- Serious AEs

- Serious study drug related AEs
- AEs leading to study drug withdrawn/interruption
- Study drug related AEs leading to study drug withdrawn/interruption
- AEs leading to study discontinuation
- Study drug related AEs leading to study discontinuation
- AEs resulting in death
- Study drug related AEs resulting in death
- AEs of Special Interest

Serious and most common non-serious AE by order of frequency (Most frequent, 2nd most frequent and 3rd most frequent) will be summarized by PT. Most common non-serious AEs are any preferred term that at least 5% of the subjects reported at least once.

Subject listings of all AEs, serious AEs, AEs leading to study drug withdrawn/interruption, AEs leading to study discontinuation, AEs resulting in death and AEs of Special Interest will be provided.

Refer to [Table 17](#) for computation of duration of AE.

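### After retreatment, the planned SOC/PT adverse-event tables cannot show how many subjects have a late-onset event of a term that also occurs during the treatment sessions

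*SAP*

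**What the plan says.** SAP section 2.1 lists long-term safety as a primary objective, and also this one: "The safety of CCH when used for retreatment in the treatment of EFP commonly known as cellulite in adult women". Under its special-interest heading, section 3.11.1 asks for "local AEs associated with the injection site (whether the site was injected in the double-blind study" or in this study. There it names acute reactions separately from chronic changes such as skin thickening and fibrosclerosis.

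Section 4.5.1.2 assigns each event to a period by its start date. After the course, "AEs with a start date on or after Day 71 of retreatment will be aligned with observational assessment visits", which gives four later periods up to Month 36.

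Section 7.7.2 then plans two kinds of output for events during and after retreatment:

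- An overall summary "by treatment sessions and time period (ie, all study periods and each study period as described in section 4.5.1.2". Its rows are counts of any, special-interest, serious, graded and fatal events and of events leading to withdrawal or discontinuation. It is given for all new events and for drug-related ones.
- Thirteen SOC/PT tables, presented "by subject category (ie, Category I, II, and overall) and each treatment sessions [TX1, TX2, TX3, and Total". The Total "includes AEs reported during Treatment Session 1, 2, and 3, and Observation Period post Day 71 of retreatment".

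The counting rule for all of these is "A subject will only be counted once per SOC and PT", with the maximum intensity kept in severity tables and the strongest association kept in causality tables. Each table shows occurrences as well as subjects.

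**The concern.** The later periods exist in the event assignment and in the overall summary, but not in the tables that name the events. In the SOC/PT tables, an event that starts months after the last injection appears only inside a Total that also holds the acute injection-period events.

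If a subject has a term during a session and a new episode of that term later, the later episode leaves the Total subject count unchanged. If it is no more severe than the first, it leaves her recorded grade unchanged too. The study follows retreated women with local safety assessments out to Month 36, so the incidence of late-onset events by term is a natural result to want from it. For such terms, the plan does not produce it.

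**Working it through.** The plan states no figure for this point, so there is nothing to reproduce. The check is whether the late subject count for one term can be recovered from the planned columns.

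**Inputs.** From section 7.7.2: the columns TX1, TX2, TX3 and Total; one count per subject and term; occurrences also shown. From section 4.5.1.2: assignment by start date. The counts below are assumed.

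**Occurrences.** Late occurrences = Total occurrences − (TX1 + TX2 + TX3 occurrences). This can be recovered.

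**Subjects.** Let A be the subjects with the term in any session and L those with a late-onset event. Total shows the size of A or L combined, so

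late subjects = Total − (size of A) + (number in both A and L).

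Neither quantity on the right, other than Total, is displayed. The three session columns overlap, so their sum is not the size of A.

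**Illustration.** Assume 100 retreated subjects. For one term, 60, 50 and 40 have one event each in TX1, TX2 and TX3. The groups are nested, and all late events fall among the same 60 subjects.

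| Late subjects | Late events each | TX1 / TX2 / TX3 subjects | Total subjects | Total occurrences |
|---|---|---|---|---|
| 0 | 0 | 60 / 50 / 40 | 60 | 150 |
| 20 | 1 | 60 / 50 / 40 | 60 | 170 |
| 10 | 2 | 60 / 50 / 40 | 60 | 170 |
| 60 | 1 | 60 / 50 / 40 | 60 | 210 |

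The subject columns are the same in every row. Occurrences give 150 − 150 = 0, 170 − 150 = 20 and 210 − 150 = 60 late events. The second and third rows agree in every cell the table would show, yet the late incidence is 20/100 = 20% in one and 10/100 = 10% in the other.

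**Cases where the count can be recovered.** If the term never occurs in a session, A is empty and Total is the late subject count. If the outcome can happen only once per subject, the columns do not overlap and Total − (TX1 + TX2 + TX3) gives it.

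**Boundary.** Section 4.5.1.2 extends Treatment Session 3 through the Day 71 visit date, and does the same for an earlier session when no further dose is given. It also opens the first observation period on Day 71. An event starting on that date therefore meets both definitions, and the subtraction above holds only apart from such events. The rules for unknown start dates in section 6.3.1.1 end Session 3 before Day 71.

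**Follow-up without its own SOC/PT column.** The share of follow-up to Day 1080 that lies after retreatment Day 71, for a course starting on study day s, is (1080 − s − 70) / (1080 − s).

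- s = 351 (the SAP's own example, section 3.1.2): 659/729 = 90%.
- s = 180 (assumed early start): 830/900 = 92%.
- s = 720 (assumed late start): 290/360 = 81%.

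These are shares of calendar time, not of events.

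**The case against.** The strongest answer is that little is hidden. The overall summary already gives subject counts for each later period: any event, special-interest, serious, each severity grade, discontinuation and death, and the same for drug-related events. Section 3.11.1 describes chronic local events under special interest, so that row may well include them. Late occurrences per term follow by subtraction, and full listings are planned. Of the thirteen SOC/PT tables, the six on drug withdrawal, study discontinuation and death are hardly touched. Serious events should rarely recur within one subject and term. The study is open-label and descriptive, so no estimate is biased.

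Most of that stands, and it limits the point. It does not remove it. The overall summary does not say which terms the late events are, occurrences are not subjects, and listings are not a planned result.

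A reader might infer that a late signal for the named chronic changes would be masked by acute reactions. The SAP does not support that. Each preferred term has its own row, and a term absent from the sessions shows directly in Total. Nor does the SAP say that acute episodes are usually the more severe.

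**Conclusion.** The point holds for preferred terms that occur both during a treatment session and, as a new episode, after retreatment Day 71. For these, the planned tables give late occurrences but not the number, percentage or severity of subjects. How many terms that affects cannot be known from the SAP; the counts above are illustrative.

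Three broader readings are not supported. Late events after re-exposure are not left unreported, since the overall summary shows them by period. The long share of follow-up after the course (about 81% to 92%, depending on the assumed start) does not measure how much information is lost. And chronic harm is not the same as late onset: because assignment is by start date, an event that begins in a session and persists stays with that session, and a new column would not move it.

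The gap is one of table layout. It is worth closing because long-term safety and retreatment safety are primary objectives and the data are already collected. It does not touch dosing or clinical management.

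**What to change.** First, amend section 4.5.1.2 so that an event starting on the retreatment Day 71 visit date belongs to one period only, and align section 6.3.1.1 with that choice.

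Then, in the part of section 7.7.2 on events during and after retreatment, add two columns to the SOC/PT tables: 'Any treatment session' and 'Observation period after retreatment Day 71', both using the boundary just set. Do this at least for all events, severity, causality, drug-related events by severity, serious events and "AEs of Special Interest". State that the count-once, worst-grade and strongest-association rules apply within each column. Use retreated subjects followed beyond retreatment Day 71 as the denominator of the observation column.

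The cost is SAP wording and two extra columns in the Module 2 shells. No new data are needed. The downside is wider tables, and persistence of session-onset events would still have to be read from AE duration.

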7.7.3. Clinical Laboratory

For Day 180 Observational Population and Prior to Day 180 Population, laboratory assessments (hematology and biochemistry) at specific visits and change from baseline at corresponding post baseline visits through Day 180 visit will be summarized by treatment arm (ie, CCH 1.68 mg, Placebo, and Overall) in double-blind studies (EN3835-302/303).

For subjects in OLR Population after retreatment, laboratory assessments (hematology and biochemistry) at specific visits and change from baseline at corresponding post baseline visits after Day 180 visits and end of treatment session assessments (ie, Day 71) will be summarized by subject category (ie, Category I, II, and Overall) using descriptive statistics.

For Day 180 Observational Population and Prior to Day 180 Population, the Screening assessments done within 14 days of/or Day 71/EOS visit in the double-blind studies will be used as baseline. The same set of tables will be reproduced for change from baseline considering Day 1 of the double-blind studies will also be presented.

For subjects in OLR Population with after retreatment, the assessments at Screening B or unscheduled visits prior to/on the first dose date of retreatment in this study will be used as baseline.

The PCI laboratory values will be summarized by counts and percentages for Day 180 Observational Population and subjects in OLR Population after retreatment, separately. Refer to [Table 14](#) for PCI criteria.

Subject listing (including urinalysis results) will be presented for all laboratory parameters for Day 180 Observational Population and for subjects in OLR Population after retreatment, separately. In addition, serum and urine pregnancy test results will be listed by subject for different populations as above.

7.7.4. Vital Signs

For Day 180 Observational Population, vital signs (systolic and diastolic blood pressure, pulse rate, respiratory rate, body temperature and body weight) at specific visits and change from baseline at corresponding post baseline visits through Day 180 visit will be summarized using descriptive statistics by treatment arm (ie, CCH 1.68 mg, Placebo, and Overall) in double-blind studies (EN3835-302/303). The same set of tables will be reproduced for change from baseline considering Day 1 of the double-blind studies will also be presented.

For subjects in OLR Population after retreatment, vital signs (systolic and diastolic blood pressure, pulse rate, respiratory rate, body temperature and body weight) at specific visits and change from baseline at corresponding post baseline visits after Day 180 visits through end of treatment session assessments will be summarized by subject category (ie, Category I, II, and Overall) using descriptive statistics.

For Day 180 Observational Population, the Screening assessments done within 14 days of/ or Day 71/EOS visit in the double-blind studies will be used as baseline. For subjects in OLR Population after retreatment, the assessments at Screening B or unscheduled visits prior to/on the first dose date of retreatment in this study will be used as baseline.

The PCI vital signs values will be summarized by counts and percentages for Day 180 Observational Population and for subjects in OLR Population after retreatment, separately. Refer to [Table 15](#) for PCI criteria.

A subject listing will be presented for all vital signs parameters for Day 180 Observational Population and for subjects in OLR Population with retreatment separately.

7.7.5. 12-Lead ECG

The investigator interpretation of ECG results (normal, abnormal not clinically significant or abnormal clinically significant) at Screening B (for Category I and II retreated subjects) will be listed for OLR Population.

7.7.6. Physical Examination

Physical examination (body system) screening results will be presented separately for Day 180 Observational Population and for subjects in OLR Population separately.

7.7.7. Immunogenicity

The immunogenicity data for subjects who entered the Open-label Period of the study will be summarized separately before retreatment using Open-label Observation Population, and after retreatment using OLR Population.

Immunogenicity Data Before Retreatment: The immunogenicity data at Screening (Day 71 of double-blind studies) and Observation Visits prior to retreatment will be summarized by Subject Category (ie, Category I, II, III, and Overall) for subjects in Open-label Observation Population.

Immunogenicity Data After Retreatment: The immunogenicity data at Screening B (screening during retreatment phase), Treatment Visits (TX2, TX3, and TX4) and Observation Visits after retreatment through end of study will be summarized for subjects in OLR Population.

The immunogenicity data of binding and neutralizing anti-AUX-I and anti-AUX-II antibodies will be summarized using the number of subjects with an immunogenicity sample, the percentage of subjects with a positive sample, and a descriptive summary of the average titer level of the positive samples at the assessment visits. The titer levels will be logarithmically transformed prior to being summarized descriptively.

The number and percentage of assayed serum samples that will detect the presence or absence of neutralizing antibodies (positive/negative) to AUX-I and AUX-II will be summarized by antidrug antibody quartiles for the retreated subjects using frequency counts and percentages at Day 71/End of Retreatment phase.

The listings of immunogenicity data will be presented separately for the All Subjects prior to retreatment and for subjects in OLR Population after retreatment.

